4.2.8.2. Analysis Methods

The primary analysis for QoL will be based on the change from baseline on the TOI score at each assessment time point, which will be summarized using descriptive statistics including mean, standard deviation, median, minimum, and maximum. The total score considering all 5 subscales as well as the 5 individual subscale sums of scores will be summarized similarly. The same analysis windows as in Table 2-1 will be used with the only exception that C1D15 is not considered as the questionnaire was not scheduled to administer during that visit.

The following supportive analyses will be conducted:

- In patients with a best response of confirmed PR or better
- In patients with a best response of confirmed MR or better

4.3.

CCI

CCI [REDACTED]
[REDACTED]

[REDACTED]
[REDACTED]
[REDACTED]

[REDACTED] [REDACTED]

[REDACTED]
[REDACTED]
[REDACTED]
[REDACTED]

- [REDACTED]
[REDACTED]
[REDACTED]

- [REDACTED]

- [REDACTED]

- [REDACTED]

[REDACTED]

- [REDACTED]

- [REDACTED]

[REDACTED]
[REDACTED]

[REDACTED]
[REDACTED]

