#### **13.3.8. Procedures for Handling Missing Data**

The procedures for handling missing data will be performed per the SAP (version 1.0).

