1. OVERVIEW AND INVESTIGATIONAL PLAN

1.1. STUDY DESIGN

KCP-330-012 is a Phase 2b, single-arm, open-label, multicenter study of Sd (selinexor 80 mg plus dexamethasone 20 mg), both dosed twice weekly, for each week of a four-week cycle, in patients with multiple myeloma (MM) previously treated with alkylating agents, glucocorticoids, lenalidomide, pomalidomide, bortezomib, carfilzomib, and daratumumab, and refractory to prior treatment with glucocorticoids, at least one immunomodulatory agent (IMiD), at least one proteasome inhibitor (PI), and the anti-CD38 mAb daratumumab (i.e., penta-refractory MM). Note: refractory is defined as $\leq 25\%$ response to therapy, progression during the previously described therapies, or progression within 60 days after completion of the therapy (per International Myeloma Working Group [IMWG] criteria 2016).

This study consists of two parts and will enroll approximately 210 patients overall. Part 1 (protocol V1.0-3.0) enrolled patients with both quad-refractory MM (i.e., previously treated with alkylating agents, glucocorticoids, lenalidomide, pomalidomide, bortezomib, carfilzomib, but not an anti-CD38 mAb, and refractory to prior treatment with glucocorticoids, at least one IMiD, and at least one PI) along with patients that had quad-refractory MM and whose disease was refractory to an anti-CD38 monoclonal antibody (i.e., penta-refractory MM). Part 2 (protocol V \geq 4.0) will enroll patients with penta-refractory MM only, and refractoriness to prior treatment with daratumumab (the only currently FDA approved anti-CD38 monoclonal antibody) is required.

The population for the primary efficacy analysis will contain only patients with penta-refractory MM enrolled in Part 2. Efficacy results for patients with quad-refractory MM and patients with penta-refractory MM enrolled in Part 1 will be analyzed separately. Safety analyses will be performed on the Part 2 patients with penta-refractory MM, the overall safety population of patients who received any amount of study treatment, presented together as well as separately by study part.

Patients receive oral selinexor 80 mg plus dexamethasone 20 mg (Sd), both dosed twice weekly, for each week of four-week cycles. Patients will receive treatment until progressive disease (PD), death, toxicity that cannot be managed by standard care, or withdrawal, whichever occurs first.

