2.2. MISSING DATA HANDLING IN DATA PRESENTATION

In general, missing baselines will not be imputed. The following approaches are default methods for missing data handling in summary tables.

- Categorical data at baseline will be summarized using counts (n) and percentages (%). Denominator will be the analysis population specified for the summary, unless otherwise specified. Missing data may be presented as a separate category.
- Continuous data: summaries will be based on observed data only.

2.2.1. Handling of Computation of Treatment Duration if Study Treatment End of Treatment Date is Missing

For the calculation of treatment duration, the date of the last dose of study treatment is equal to the date of last study treatment dosing reported on study treatment dosing form. If all the dosing dates are missing, then the duration is missing.

The last dose intake should be clearly identified on the eCRF dosing page and should not be approximated by the last returned package date.

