4. EFFICACY

Patient response at each time point will be assessed centrally by an IRC according to the IMWG response criteria (*Kumar 2016*) for MM. Unless otherwise specified, MM response assessment refers to assessment determined by IRC. The primary endpoint (ORR) is based on these IRC assessed responses in the mITT population.

Documentation of response requires two consecutive readings of the applicable disease parameter (serum M-protein, urine M-protein, serum FLC, or quantitative immunoglobulin level), performed at any time with no minimum interval required between the two readings. The date of response or PD will be assigned to the earlier date of the two independent samples, unless PD is based on an unambiguous criterion such as a new plasmacytoma lesion.

If a patient had one PD assessment but was not subsequently confirmed, unless IRC considers the progression assessment unambiguous, it is not considered a PD (*Kumar 2016*).

Unless otherwise specified, efficacy analyses will use the mITT population. Analyses for the primary efficacy endpoint of ORR and the key secondary efficacy endpoints of DOR, CBR, and duration of clinical benefit will be repeated in the other efficacy populations and additional analysis populations. If relevant, selected efficacy analyses for other efficacy endpoints will be repeated in selected additional analysis populations.

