	Day -21 to Day -1	Day 1	Day 3 ¹⁴	Day 8	Day 15	Day 1	Day 15	Day 1	≤ 14 Days Post Last Dose	30 Days Post-Last Dose	Every 3 mo.
		-1 day	+1 day	± 1 day	± 1 day	± 2 days	± 2 days	± 2 days		+ 7 days	± 14 days
Serum FLC ⁹	X	X			X	X	X	X	X		X
β ₂ -microglobulin	X								X		
Skeletal survey ¹⁰	X					(X)		(X)	X		(X)
Plasmacytoma assessment ¹¹	X					(X)		(X)	X		(X)
CCI											
CCI											
FACT-MM questionnaire	X					X		X	X		
Study treatment dosing		Selinexor 80 mg + dexamethasone 20 mg (both twice weekly) for 4 weeks (each week) of 4-week cycles									
Adverse events ¹⁶	X	X	X	X	X	X	X	X	X	X	
Concomitant medications	X	X	X	X	X	X	X	X	X		

Activity/Assessment	Screening	Cycle 1				Cycle 2		Cycles ≥ 3	End-of-Treatment (EoT) Visit	Safety Follow-up Call	Durability of Response and Survival Follow-up ¹⁵
	Day -21 to Day -1	Day 1	Day 3 ¹⁴	Day 8	Day 15	Day 1	Day 15	Day 1	≤ 14 Days Post Last Dose	30 Days Post-Last Dose	Every 3 mo.
		-1 day	+1 day	± 1 day	± 1 day	± 2 days	± 2 days	± 2 days		+ 7 days	± 14 days
Nutritional consultation	X										
Telephone contact ¹⁴			X							X	X
Antineoplastic therapy after EoT									X	X	X

(X) indicates that additional information is provided in the footnotes. Merged cells indicate that the procedure may be performed during either Screening or the CID1 visit.

Abbreviations: BSA = body surface area; ECG = electrocardiogram; ECOG = Eastern Cooperative Oncology Group; EoT = End of Treatment; Ig = immunoglobulin; MM = multiple myeloma; SPEP = serum protein electrophoresis; UPEP = urine protein electrophoresis; CBC = complete blood count; FLC = free light chain.

¹ Prior to the first study-specific measure.

² Including details of all prior anti-myeloma therapies. Includes baseline symptoms as well as a detailed history of prior cancer therapies, especially MM therapies, including start and stop dates, disease progression during or after therapy, as well as discontinuations due to intolerability or any other serious illness.

³ Body Surface Area (BSA) will be calculated by *Dubois 1916* or *Mosteller 1987* method during Screening and prior to any dose escalation. No patient may receive a dose of selinexor > 70 mg/m².

⁴ Complete physical examination (PE) during Screening and EoT visit. Limited PEs during the study should be symptom directed. All PEs to include vital signs (blood pressure, pulse and body temperature).

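### Quality of life is summarised visit by visit on returned questionnaires only, so if patients leave treatment as they decline, the later means will understate that decline

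*SAP*

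**What the plan says.** **Estimator.** SAP 4.2.8.2: "The primary analysis for QoL will be based on the change from baseline on the TOI score at each assessment time point". The change is to be "summarized using descriptive statistics including mean, standard deviation, median, minimum, and maximum". Protocol 13.3.4 names paired t-tests on the change in TOI, which likewise use only patients with both readings.

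**Population and missing data.** SAP 4: "Unless otherwise specified, efficacy analyses will use the mITT population". SAP 2.2 adds "Continuous data: summaries will be based on observed data only" and "In general, missing baselines will not be imputed". Protocol 13.3.8 leaves missing-data handling to the SAP. A patient may therefore be in the mITT population and contribute nothing to a given visit mean.

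**Schedule.** In SAP Table 7-1 the "FACT-MM questionnaire" row is marked at screening, Day 1 of Cycle 2 and later cycles, and end of treatment (EoT). The three-monthly follow-up column is empty.

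**Why patients stop.** SAP 1.1: "Patients will receive treatment until progressive disease (PD), death, toxicity that cannot be managed by standard care, or withdrawal, whichever occurs first".

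**Supportive analyses.** The two visible ones in SAP 4.2.8.2 are in patients with confirmed PR or better and confirmed MR or better. For overall survival, SAP 4.2.7.2 also lists patients with SD or worse, including the non-evaluable. The visible QoL section has no such group.

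**The concern.** Each later visit mean is taken over a smaller group: patients still on treatment who return a form. Three of the stopping reasons (progression, unmanageable toxicity, approaching death) could plausibly go with a falling TOI. If they do, the decliners leave the average and the curve flattens without anyone's quality of life changing. The responder analyses select in the same direction.

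Early loss may not be rare. In Protocol Table 3, 5 of 30 Part 1 penta-refractory patients had PD as best response and 7 were non-evaluable, together 12/30 = 40%. That is not a dropout rate, but it suggests many patients with few cycles.

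What is at stake is interpretation. SAP 4.2.8.1 says the questionnaire is to assess quality of life and its potential to improve over the study. In a single-arm trial with this table alone, a reader could not separate stability from attrition.

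**Working it through.** The plan gives no expected QoL effect, variability or dropout rate, so there is no figure to reproduce. Every slope and dropout input below is an assumption. Only N = 122 comes from the documents (Protocol synopsis, Study Numbers).

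**Check 1: dropout depends on the last observed score.** Change for patient i after c cycles = b_i × c + error, with b_i ~ N(-2, 2.5²) and error SD 6. The per-cycle dropout probability is 22% at zero change, and its odds rise 10% per point lost on the last score. The true mean is -2c.

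| Cycles | True mean | Observed mean | Share contributing | Patients of 122 |
|---|---|---|---|---|
| 1 | -2 | -2.0 | 78% | 95 |
| 3 | -6 | -4.6 | 39% | 48 |
| 5 | -10 | -2.3 | 17% | 21 |
| 7 | -14 | +4.2 | 9% | 11 |

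The gap at cycle 3 is 6 - 4.6 = 1.4 points. Varying the assumptions changes the cycle 7 value:

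| Setting | Observed mean at cycle 7 (true -14) |
|---|---|
| No link between score and dropout | -13.9 |
| 10% per point, slope SD 1.5 | about -5.2 (to about -5.5 in repeat runs) |
| 5% per point, slope SD 2.5 | -3.0 |
| 10% per point, slope SD 2.5 | +4.2 |

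**Check 2: dropout depends on the underlying slope.** b_i ~ N(-2, 3²) per 28 days, with discontinuation hazard 0.2 × exp(-β(b_i + 2)) per 28 days.

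| Day | Cohort mean | Observed, β = 0.15 | Observed, β = 0.3 |
|---|---|---|---|
| 57 | -4.0 | -2.9 | -1.9 |
| 85 | -6.0 | -3.6 | -1.8 |
| 113 | -8.0 | -3.9 | -1.3 |
| 169 | -12.0 | -3.5 | +0.9 |

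With β = 0 the two agree (-12.1 and -12.1 at Day 169). The early gaps are larger in this model: 6.0 - 3.6 = 2.4 and 6.0 - 1.8 = 4.2 points at Day 85.

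**Check 3: two groups, closed form.** 25% are stable with median 7 cycles on treatment, and 75% lose 3 points per cycle with median 2 cycles. With A = 0.25 × 2^(-c/7) and B = 0.75 × 2^(-c/2), observed mean = -3c × B/(A + B) and cohort mean = -0.75 × 3c.
- c = 5: A = 0.152, B = 0.133; observed -15 × 0.133/0.285 = -7.0; cohort -11.25.
- c = 8: A = 0.113, B = 0.047; observed -24 × 0.047/0.160 = -7.0; cohort -18.

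Here the curve goes flat but does not turn upward.

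**Check 4: does the EoT questionnaire repair this?** I added an EoT form from every leaver 7 days after the last dose, using the SAP Table 2-1 windows. In check 2, Day 169 moves only from -3.5 to -3.9 (β = 0.15) and from +0.9 to +0.4 (β = 0.3). Each form counts in at most one window. After Day 57 the windows cover 13 of every 28 days (46%), so about 54% of possible EoT days map to no visit. SAP 4.2.8.2 drops only C1D15, yet FACT-MM is not scheduled at C2D15 either. The Day 43 window would therefore hold mainly leavers' EoT forms (about 8 of 122 in the simulation) and could show a spurious dip.

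**Check 5: would a repeated-measures model help?** On the strong setting of check 1, an unstructured repeated-measures likelihood estimate recovered about -2, -6, -10 and -14 after 1, 3, 5 and 7 cycles. Its SD is about 3 points at cycle 5 and 8 at cycle 7, so 95% limits are roughly ±1.96 × 3 = ±6 and ±1.96 × 8 = ±16. Dropout in that simulation depends only on observed scores, which favours the model.

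**The case against.** The strongest case against is that this is a descriptive secondary endpoint for which the SAP plans no test or claim, and that a while-on-treatment summary is a legitimate, if limited, target. The full-cohort comparator is itself debatable, since it assigns scores to patients who may have died. Without a control arm, no estimator could support a comparative QoL statement. All of this stands, and it limits the weight of the point.

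The plan also has some safeguards. SAP 2.1 requires n with every continuous summary, SAP 3.1 tabulates reasons for stopping treatment, and an EoT form is scheduled. But n alone does not separate patients off treatment, dead, not yet due or simply without a form, and check 4 shows that the EoT form changes little.

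Two stronger readings are tempting. A reader might infer that the patients missing at later visits are mainly those whose scores are falling. The documents do not say so. Some will be missing only because the primary snapshot is taken once all patients have completed the Cycle 2 assessments (SAP 1.6), which is unrelated to decline. A reader might also infer that the curve will show improvement, or that the endpoint can support no statement at all. The sign change appears only in the stronger settings: in check 1 it rests on about 11 patients, and with no link there is no bias.

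Finally, SAP 4.3 and the protocol text after the QoL paragraph are redacted, so a sensitivity analysis there cannot be excluded.

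**Conclusion.** The point holds as a conditional one. If leaving treatment is related to declining quality of life, the planned by-visit means will understate decline at later cycles, and nothing in the visible text would reveal it. Under the assumed inputs of check 1, the observed mean at cycle 7 runs from about -14 (no link) through about -5.5 to -3 (weaker settings) to about +4 (strong link), against a true -14. Over the first three cycles, where most data lie, that model's gap is 0 to 1.4 points. The slope-driven model gives more by Day 85 (2.4 to 4.2), so the early reassurance depends on the dropout mechanism. The size is illustrative because the documents supply neither the slope nor the link. The consequence is confined to how a statement that quality of life was maintained or improved can be read. The ORR analysis is untouched.

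**What to change.** Keep the descriptive table and add the following to SAP 4.2.8.2:

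1. For each visit, the number of questionnaires completed, the number of patients still on treatment and the number alive, with patients not yet at that visit because of the data cut counted separately.
2. Mean TOI change by last cycle completed (for example C3 or earlier, C4 to C6, C7 or later).
3. The EoT questionnaire as its own time point, outside the by-visit windows. This also removes the Day 43 artefact.
4. A repeated-measures mixed model of TOI change, with baseline TOI and visit as covariates and all observed post-baseline scores, giving 95% confidence intervals. Report it beside the descriptive means and only for visits with adequate numbers. Describe it as an estimate that assumes dropout is explained by observed scores and that does not describe quality of life after death.

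The cost is SAP wording and modest programming on data already collected. The downsides are wide intervals at late cycles and the missing-at-random assumption, which cannot be verified, although item 2 lets a reader see how far change differs by time of dropout. Items 1 to 3 need no model and would by themselves remove most of the risk of misreading.

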5. SAFETY

Safety analyses will use the safety population with the outputs presented by the following groups:

- Overall safety population
- The subset of safety population from Part 2
- The subset of safety population from Part 1

Safety analyses will be based on the reported AEs and other safety information, such as 12-lead electrocardiogram (ECG), ophthalmic exam, clinical laboratory assessments including hematology, serum chemistry, coagulation parameters, and urinalysis, vital signs, physical examination, and pregnancy testing.

Observation period

The observation period will be divided into the following periods:

- The pre-treatment period is defined as the time from the signed informed consent date up to first dose of study treatment.
- The treatment period is defined as the time from first dose of study treatment to last dose of study treatment + 30 days inclusive.
- The post-treatment period is defined as the time beyond the treatment period.

The on-study observation period is pre-treatment, treatment, and post-treatment period.

General rules

All safety analyses will be performed using the following common rules:

- Safety data in patients who do not belong to the safety population (e.g., enrolled but did not receive any dose of study treatment, partial or complete) will be listed separately.
- The baseline value is the last available value before the first dose of study treatment.
- The analyses of the safety variables will be essentially descriptive and no systematic testing is planned.

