5.3.2. Analysis of Laboratory Variables

Whenever applicable, severity of selected clinical laboratory measures will be determined based on the CTCAE criteria. The worst toxicity grade in hematology and chemistry will be summarized by toxicity grade. Shift tables that present changes from baseline to worst on-study and baseline to last on-study values relative to CTCAE classification ranges will be presented.

For several key laboratory parameters (e.g., sodium, creatinine, platelet, hemoglobin, WBC, BUN-to-creatinine ratio, urea-to-creatinine ratio), box plots on measurements over time may be presented.

A listing of possible Hy's law cases (ALT or AST > 3 x upper limit of normal [ULN] with simultaneous total bilirubin > 2 x ULN) will be presented. The elevations of ALT/AST and total bilirubin must occur within 2 days of each other.

Thresholds/Range analyses for selected laboratory, vital signs, and ECG parameters will be conducted. Please refer to Appendix 7.2 for the definitions on thresholds/ranges for selected parameters. The number and percentage of patients classified into each category based on worst values will be presented.

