5.4. VITAL SIGNS, ECOG, AND PHYSICAL EXAMINATION VARIABLES

Full physical examinations with vital signs are performed only during screening and end-of-treatment (EoT) visits, including height (without shoes) in centimeters (cm) [measured during screening visit only], weight (indoor clothing without shoes) in kilograms (kg), temperature, heart rate, systolic and diastolic blood pressure, and oxygen saturation.

At other visits, symptom-directed physical examinations are conducted with vital signs (temperature, heart rate, systolic and diastolic blood pressure).

An ECOG score assessment with grades 0-5 will be performed during screening, day 1 of each cycle, and the EoT visit.

Shift tables that present changes from baseline to worst on-study and last on-study for systolic blood pressure, diastolic blood pressure, and ECOG performance status values will be produced.

Abnormal vital signs results will be summarized in the threshold/range analyses as defined in Appendix 7.2.

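### The SAP counts pre-dose values as on-study, so its worst and last on-study shift tables can show false worsening, hide improvement, or report patients with no post-dose value as unchanged

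*SAP*

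**What the plan says.** SAP section 5 divides observation time into three periods. The first begins at consent: "The pre-treatment period is defined as the time from the signed informed consent date up to first dose of study treatment". The treatment period runs from first dose through last dose + 30 days, and everything later is post-treatment. The SAP then joins all three: "The on-study observation period is pre-treatment, treatment, and post-treatment period". This is its only definition of on-study. The general rules in the same section add: "The baseline value is the last available value before the first dose of study treatment".

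Section 5.3.2 plans, for laboratory data, "Shift tables that present changes from baseline to worst on-study and baseline to last on-study values relative to CTCAE classification ranges". Section 5.4 plans the same comparison for "worst on-study and last on-study for systolic blood pressure, diastolic blood pressure, and ECOG performance status values will be produced". Neither section limits the values to those taken after dosing.

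Two other summaries in section 5.3.2 name no period at all: the worst toxicity grade in haematology and chemistry, and the Table 7-2 threshold counts ("The number and percentage of patients classified into each category based on worst values will be presented").

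**The concern.** A shift table is meant to show what happened after treatment began. Under the SAP's definition, every value from consent onward is eligible to be the worst or last one, including the baseline value and anything measured before it. The after column of the table can then be filled by a measurement that preceded the drug.

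The trial has no control arm, so change from baseline is the main way to see laboratory, blood-pressure and performance-status effects. An error here can go either way: it can create a worsening that did not follow treatment, or conceal an improvement or a missing assessment.

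**Working it through.** No figure in the plan can be reproduced here, so the check applies the definitions literally and then asks where the schedule lets them matter.

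**Which variables have a pre-dose value earlier than baseline?**

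- *Blood pressure.* SAP Table 7-1 schedules a full examination at Screening and a symptom-directed one at C1D1, and footnote 4 requires blood pressure at every examination. When the C1D1 reading is taken before dosing it is the baseline, and the Screening reading is an additional on-study value.
- *ECOG.* SAP 5.4 and Protocol 9.1.5 call for Screening and Day 1 of each cycle. Footnote 5 of the schedule allows Screening or pre-dose C1D1. The route is open when both are done.
- *Laboratory tests.* Footnote 5 requires one pre-dose blood count and one complete chemistry. If only one exists, it is the baseline and cannot create a worsening. The route opens only with an extra pre-dose sample, which Protocol 13.3.7.2 anticipates by preferring Day 1 and falling back on Screening.

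**Does another rule exclude pre-dose values?** The windows in SAP 2.6 separate baseline from later visits, but only for data summarised or plotted by time point. They do not govern worst or last values.

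**Consequence 1: false worsening.** Illustrative platelet counts (×10⁹/L), graded by SAP Table 7-2 with an assumed lower limit of normal of 150:

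| Value | Count | Grade |
|---|---|---|
| Screening | 60 | 2 |
| C1D1 baseline | 80 | 1 |
| Post-dose | 78, 90, 85 | 1, 1, 1 |

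Literal rule: the worst of all values is Grade 2, so the shift is 1 to 2. Post-dose values only: 1 to 1. The same happens for systolic pressure if Screening is above 140 mmHg and every later reading is at or below it. (140 is a Table 7-2 cut point; section 5.4 gives no categories for its own shift table.)

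**Consequence 2: hidden improvement.** This needs only one pre-dose value. Baseline platelets 60 (Grade 2), post-dose 80 and 90 (both Grade 1). Literal rule: the worst includes the baseline itself, so the shift is 2 to 2. Post-dose values only: 2 to 1. Under the literal rule no patient's worst value can ever be better than baseline.

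**Consequence 3: no post-dose value.** The only on-study values are then pre-dose. The last one is the baseline, so the last-value shift is no change; with a single pre-dose value the worst-value shift is no change too. SAP 3.1.2 admits a patient to the safety population on any post-baseline safety information, which need not be a laboratory value, blood pressure or ECOG score.

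**A ceiling for blood pressure.** Assume one Screening reading, one baseline and k post-dose readings, all exchangeable, with no drug effect. A false worsening from Screening requires the Screening reading to be the most extreme of k + 2 readings, which has probability 1/(k + 2).

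- Stops in Cycle 1 after Day 15 (Day 8, Day 15, end of treatment): k = 3, 1/5 = 20%.
- Stops after Cycle 3 Day 1 (adding Cycle 2 Days 1 and 15 and Cycle 3 Day 1): k = 6, 1/8 = 12.5%.
- k = 12: 1/14 = 7%.

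A simulation of 400,000 draws gives 20.0%, 12.4% and 7.2%. The chance of an actual category shift is lower, because the reading must also cross a boundary.

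**The case against.** The strongest reply is that no programmer would do this. A change from baseline to a worst on-study value has a direction, and Protocol 13.3.7.2 and 13.3.7.3 speak of change from baseline to each on-study evaluation, which suggests post-baseline. That lowers the practical risk. It does not remove it: the protocol never defines the term, and the SAP defines it the other way.

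The reply is also right to limit how far the point reaches. A reader might infer more in five places, and the documents do not support it:

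- *That laboratory worsening is inflated across the trial by some calculable percentage.* Any such figure assumes two pre-dose samples for every patient, whereas footnote 5 requires one.
- *That false new Grade 3 anaemia appears.* Grade 3 is below 80 g/L in Table 7-2. Inclusion criterion 13 requires at least 8.5 g/dL (85 g/L), or above 8.0 g/dL (80 g/L) with Medical Monitor approval, so a qualifying Screening value cannot be Grade 3.
- *That the 16 of 78 (21%) non-evaluable patients in Protocol Table 3 show how many lack post-dose data.* That is a response category. Limited chemistry is due at Day 8, before the first full post-dose myeloma assessment at Cycle 2 Day 1.
- *That values under later therapy distort the tables.* No blood count, chemistry or ECOG score is scheduled after the end-of-treatment visit, and follow-up examinations occur only if clinically appropriate.
- *That the definition governs Table 7-2.* That text says worst values, not on-study values. It leaves a gap but does not state the wrong rule.

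Finally, SAP section 5 describes the safety analyses as essentially descriptive, without systematic testing.

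**Conclusion.** The point stands as an error in the rule for descriptive tables. Followed as written, SAP 5, 5.3.2 and 5.4 give wrong shifts. The most general effect is that improvement is hidden, since one pre-dose value is enough for that. False worsening is clearest for blood pressure, conditional for ECOG, and confined to patients with extra pre-dose samples for laboratory tests. Patients without a post-dose value can be shown as unchanged.

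The documents do not give the number of patients affected. The blood-pressure figures are ceilings that rest on exchangeable readings, no drug effect and a C1D1 reading before dosing. The platelet counts and the lower limit of 150 are illustrative assumptions. The primary ORR test is unaffected, and so are treatment-emergent adverse events, which have their own post-dose definition in SAP 5.1.1.

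**What to change.** In SAP 5.3.2 and 5.4, state that worst and last values for shift tables are those measured after the first dose and through the end of the treatment period already defined (last dose + 30 days). State that the denominator is patients with a baseline and at least one post-dose value of the parameter, and show how many are excluded. Apply the same window to the worst-grade summary and the Table 7-2 counts, so that all these tables describe the same period. List values after last dose + 30 days rather than tabulating them.

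The cost is a few sentences of SAP text and one programming filter. No data collection changes. Little laboratory information leaves the tables, because no safety laboratory tests are scheduled after the end-of-treatment visit.
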